### 8.2.2.1. Planned Efficacy Statistical Analyses

Statistical Analyses –Mixed Model with Repeated Measures–	
Endpoint(s)	

 
Change from baseline in DAS28 (CRP)
 
	
Model Specification	

 
This endpoint will be analyzed using a mixed-models repeated measures (MMRM) approach.
 
Analysis will include the following fixed effects: 
 
Dose group as a categorical variable
 
Visit as a categorical variable
 
Baseline DAS28(CRP) as a continuous variable
 
Dose-by-visit interaction
 
Visit-by-baseline interaction
 
 
 
An unstructured variance structure will be used to model the within-patient errors.
 
Analyses will be done with the MIXED Procedure in SAS, using the Kenward-Roger option to estimate denominator degrees of freedom and standard errors.
 
	
Model Checking & Diagnostics	

 
Refer to Appendix 8: Model Checking and Diagnostics for Statistical Analyses.
 
	
Model Results Presentation	

 
LSmeans for each dose will be presented along with the associated 95% CI.
 
Point estimates and their associated 95% CI will be calculated for the differences between each GSK3196165 dose group and Placebo (GSK3196165 – Placebo).
 
The primary treatment comparison will be the contrast between the GSK3196165 groups to placebo.
 
	

Statistical Analyses – Dose response Analysis –	
Endpoint(s)	

 
Change from baseline in DAS28 (CRP) at Week 12.
 
	
Model Specification	

 
The following non-linear models will be fitted exploratory.
 
	
$DAS28(CRP)_i = E_0 + \frac{E_{\max} Dose_i}{Dose_i + ED_{50}} + \varepsilon_i$	
$DAS28(CRP)_i = E_0 + \frac{E_{\max} Dose_i^B}{Dose_i^B + ED_{50}^B} + \varepsilon_i$	
$DAS28(CRP)_i = E_0 + E_1 \times Dose_i + \varepsilon_i$	

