
 
The notation in the formula is as below: 
 
Subscript i denotes i-th subject.
 
<math>E_0</math> : Response at dose 0 (placebo)
 
<math>E_{\max}</math> : Maximum effect (for reduction, <math>E_{\max} \leq 0</math>; for increase, <math>E_{\max} \geq 0</math>)
 
<math>ED_{50}</math> : Dose at which 50% of maximum effect is reached
 
 
 
	

Statistical Analyses – Dose response Analysis –
--

- $B$  : a slope factor
- $E_1$  : Coefficient of a linear model.
- $\varepsilon_i$  : Residual error following  $N(0, \sigma^2)$
- The dose will be set to zero for all placebo data.
- Starting values for the iterations will be chosen based on the observed data as appropriate. For example;
  - $E_0$  : Mean in Placebo
  - $E_{max}$  : Mean difference between 180 mg and Placebo (180 mg – Placebo)
  - $ED_{50}$  :  $90 (= (180 - 0) / 2)$
  - $B = 1$
- Each of the models will be fitted to the data and their fit compared using the Akaike information criteria (AIC).
- The model with the smallest AIC will be selected as the final model for inference.

Model Checking & Diagnostics
---

- Refer to Appendix 8: Model Checking and Diagnostics for Statistical Analyses.

Calculation procedure for the 95% CIs using a bootstrap method
---

- The 95% CIs will be calculated in accordance with the following procedure.
  1. Recreate the dataset by sampling with replacement from the original dataset by dose group.
    - Use a PROC SURVEYSELECT with SEED = 161216 to generate the bootstrap dataset
  2. Fit the final dose response model to the dataset in step 1. Estimate the parameters of interest  $\hat{\theta}_1$  and compute  $g(\hat{\theta}_1)$  {g is any arbitrary function.}
  3. Repeat steps 1-2, for  $b = 1, 2, \dots, B$  ( $B=10,000$ ) to obtain  $\hat{\theta}_1, \hat{\theta}_2, \dots, \hat{\theta}_B$  and compute  $g(\hat{\theta}_1), g(\hat{\theta}_2), \dots, g(\hat{\theta}_B)$ .
  4. Select 2.5% quantile of the  $\hat{\theta}_b$  and  $g(\hat{\theta}_b)$  as the lower limit and 97.5% quantile as the upper limit.

Model Results Presentation
-----------------------------------

- The result of the final model will be presented.
- The estimates of model parameters and their 95% CI will be presented.
- From the fitted model, predictive responses for each of the doses will be calculated along with 95% CI.

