- The differences between each GSK3196165 dose and Placebo and their 95% CI will be calculated from the fitted model.
- A plot of the residuals versus predicted values will be examined to assess distributional assumptions.
- The results of the other models will be shown as only SAS outputs.

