## 11.8. Appendix 8: Model Checking and Diagnostics for Statistical Analyses

### 11.8.1. Statistical Analysis Assumptions

Endpoint(s)	
 
Change from baseline in DAS28(CRP), DAS28(ESR), SDAI, CDAI and FACIT-fatigue
 

Analysis	
 
MMRM
 

	
 
The Kenward and Roger method for approximating the denominator degrees of freedom and correcting for bias in the estimated variance-covariance of the fixed effects will be used.
 
An unstructured covariance structure for the R matrix will be used by specifying 'type=UN' on the REPEATED line. 
 
In the event that this model fails to converge, alternative correlation structures may be considered such as CSH or CS.
 
 
 
Akaike's Information Criteria (AIC) will be used to assist with the selection of covariance structure.
 

Endpoint(s)	
 
Change from baseline in DAS28(CRP) at Week 12
 

Analysis	
 
Dose response analysis
 

	
 
Distributional assumptions underlying the model used for analysis will be examined by obtaining a plot of the residuals versus the fitted values to gain confidence that the model assumptions are reasonable.
 

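### The dose-response bootstrap refits only the AIC-selected curve, so its 95% intervals ignore model selection and can be far too narrow at 45 and 90 mg

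*SAP*

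**What the plan says.** The dose-response part of SAP Section 8.2.2.1 introduces three candidates for the Week 12 change in DAS28(CRP), namely Emax, sigmoid Emax and a straight line: "The following non-linear models will be fitted exploratory". Their fit is compared by AIC, and "The model with the smallest AIC will be selected as the final model for inference".

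The bootstrap resamples within dose group. Step 2 is "Fit the final dose response model to the dataset in step 1". Steps 1 and 2 are repeated 10,000 times, and the 2.5% and 97.5% quantiles become the interval limits. The AIC comparison is not part of the loop.

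Three kinds of interval follow. For parameters, "The estimates of model parameters and their 95% CI will be presented". Predicted responses at each dose also get 95% intervals. For contrasts, "The differences between each GSK3196165 dose and Placebo and their 95% CI will be calculated from the fitted model". They are reported in Table 2.4 and Figure 2.4. The models that were not selected appear only as SAS output.

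SAP Section 11.8.1 adds only a residual plot for this analysis. Its one convergence rule, "In the event that this model fails to converge, alternative correlation structures may be considered such as CSH or CS", concerns the MMRM covariance structure. The MMRM in Section 8.2.2.1 uses dose as a category, and from it "Point estimates and their associated 95% CI will be calculated for the differences between each GSK3196165 dose group and Placebo".

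**The concern.** The interval should reflect the whole procedure that produced the estimate, and that procedure includes choosing the curve. Here the choice is made once on the observed data and then held fixed, so its uncertainty drops out.

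This matters most when the line is picked. Each resample then estimates one slope, and the 45 and 90 mg effects are fixed fractions of the 180 mg effect whatever the subjects at 45 and 90 mg show. That precision is earned only if the line is true. If the true curve saturates, the lower-dose effects are both understated and given tight intervals.

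The report would also hold two 95% intervals for essentially the same Week 12 contrasts, one from the MMRM (Table 2.3) and a much narrower one from the dose-response model (Table 2.4). The narrower one would be the less reliable, and nothing requires a note saying so.

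**Working it through.** **Inputs from the documents.** 40 subjects, 1:1:1:1 at 0, 45, 90 and 180 mg (Protocol 9.2); three models, smallest AIC, resampling by dose group, percentile limits (SAP 8.2.2.1). Neither document gives an SD, effect size, expected width or coverage for this analysis, so there is no stated figure to reproduce.

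**Step 1: the design alone.** The mean dose is 78.75 mg. The squared deviations are 6201.5625 + 1139.0625 + 126.5625 + 10251.5625 = 17718.75. With 10 per arm and a common SD, the standard error of a dose–placebo difference under the line is dose/√(10 × 17718.75) = dose/420.94 SD. A direct comparison of two arms has √(2/10) = 0.447 SD.

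| Dose | Line | Direct | Ratio |
|---|---|---|---|
| 45 mg | 0.107 | 0.447 | 4.2 |
| 90 mg | 0.214 | 0.447 | 2.1 |
| 180 mg | 0.428 | 0.447 | 1.05 |

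**Step 2: why AIC often picks the line.** With AIC = N ln(RSS/N) + 2k and N = 40, Emax (one more parameter) wins only if it cuts the residual sum of squares below exp(−2/40) = 0.951 of the line's, a cut of about 4.9%. Assume a true Emax curve with ED50 45 mg, differences of −0.75, −1.00 and −1.20, and SD 1.2. The between-dose sum of squares of the true means is 0.8269, of which a line explains 107.4375²/17718.75 = 0.6514. The lack of fit is 10 × 0.1754 = 1.75, against expected within-group variation of 36 × 1.44 = 51.8, or about 3.4%. On average the misfit is too small to overturn the line.

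**Step 3: what the line then does.** The best line through those true means has slope −107.4375/17718.75 = −0.00606 per mg. It gives −0.27 at 45 mg (true −0.75), −0.55 at 90 mg (true −1.00) and −1.09 at 180 mg (true −1.20). In units of its own standard error (1.2 × 0.107 = 0.128 at 45 mg; 0.257 at 90 mg; 0.513 at 180 mg), the errors are about 3.7, 1.8 and 0.2. So the damage is at the lower doses.

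**Step 4: simulated coverage.** 12 scenarios, 1,500 trials each, 500 resamples per trial, normal errors, 10 per arm. Least-squares fits with ED50 and B on a grid; Monte Carlo error about 1.3 points or less. The six saturating scenarios are: ED50 45 mg with −1.2 at 180 mg and SD 1.0, 1.2 and 1.5; and at SD 1.2, ED50 10 mg and ED50 90 mg with −1.2, and ED50 45 mg with −0.6. The 180 mg effect is thus 0.5 to 1.2 SD. Coverage of the dose–placebo difference at 45 / 90 / 180 mg:

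| Assumed truth | As written | AIC choice repeated in each resample |
|---|---|---|
| Six saturating scenarios | 37–57 / 63–78 / 89–91% | 86–92 / 92–94 / 90–93% |
| Truly linear | 86–87 / 87–88 / 91–93% | 96–97 / 94–95 / 92–93% |

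In the six, the line was picked in 40–82% of trials, and the 45 mg interval excluded the observed 45 mg–placebo mean difference in 30–51%. With a 180 mg effect of 2 SD, coverage as written was 75/76/92% (ED50 45 mg) and 91/90/92% (ED50 10 mg). With no effect at any dose it was about 91%.

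**Step 5: cross-check.** A separately coded simulation of the Step 2 case (1,500 trials, 1,000 resamples) picked the line in 61% of trials. Coverage was 38/67/91% as written and 92/95/93% with re-selection. Median widths were 0.54/1.07/1.83 and 1.53/1.71/1.93 DAS28 units. Intervals for predicted responses were less affected: 85% against 94% at 45 mg.

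**Step 6: separating the causes.** With Emax fixed in advance, the same percentile bootstrap covered 91–93% at 45 mg in the six scenarios, so small-sample bootstrap error explains only a few points. The rest comes from choosing a curve, sometimes the wrong one, and then treating it as known.

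**The case against.** The strongest case is that little hangs on these intervals. The primary objectives are PK and safety, no hypothesis is tested, sample size rests on feasibility, and the models are labelled exploratory. Readers also get raw mean changes with intervals (Figure 2.1), MMRM differences (Table 2.3, Figure 2.3), residuals (Figure 2.5) and output from all three models. This stands and limits the harm. It does not make the intervals correct. The dose-response analysis is pre-specified in Protocol 9.4.4, and without formal tests the intervals are the efficacy inference.

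Other points stand in part:

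- The ratio of 4.2 holds for any straight-line fit, including a correctly pre-specified one. It shows what assuming the line buys; the cost of selection is in Steps 4 to 6. The 0.447 SD comparator is also unadjusted, whereas the MMRM adjusts for baseline.
- Repeating the selection leaves the point estimates alone. In one run of the Step 2 case the mean 45 mg estimate was −0.59 against a true −0.75, before and after. The change repairs the intervals only.
- Conditional parameter intervals would sit beside re-selected intervals for the same quantity. When the line is picked, median widths for the placebo response are 1.07 (as E0) and 1.30 (as a prediction). A label explains this but does not remove it.
- The simulations used grid fits, which always return an answer. In one set of runs 48–64% of Emax and 65–77% of sigmoid resample fits ended on the grid boundary. Counting all of those as non-converged cut re-selected 45 mg coverage in four saturating scenarios from 87–91% to 73–87%. A similar check found 74–88%, against 40–58% as written. The gain survives but shrinks.

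**Conclusion.** The concern holds. The SAP chooses among three curves and computes intervals as if it had not, and nothing elsewhere in the documents allows for the choice. The constraint on the 45 and 90 mg effects when the line is picked follows from the design alone.

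The coverage figures rest on assumed curves, effects and SDs and are illustrative: roughly 40–60% at 45 mg and 60–80% at 90 mg for moderate saturating effects, and still below nominal when the line is true. The mechanism is certain; the size in this trial is not. The 180 mg interval is little affected. The analysis is exploratory and the MMRM offers intervals free of curve selection, so this should be corrected but does not threaten the trial's main conclusions.

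**What to change.** Replace bootstrap step 2 with wording such as:

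> Fit all three models to the resampled dataset, select the model with the smallest AIC among those that converge, and compute from it the predicted response at each dose and the dose–placebo differences. Separately, fit the final model to the same resampled dataset to obtain its parameters.

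In step 4, take the quantiles for predictions and differences over the re-selected fits and those for parameters over the fixed-model fits. Label the parameter intervals *conditional on the selected model*. Report how many resamples chose each model and how many fits did not converge. State whether a fit at a parameter bound counts as converged, since the improvement depends on it. The line has a closed form, so every resample has at least one eligible model.

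The cost is a few sentences, three fits per resample instead of one, and a footnote. The downside is width: in the ED50 45 mg, SD 1.2 case the median 45 mg interval grows from 0.55 to 1.54 DAS28 units, against 2.16 for a categorical t interval. Coverage comes near 95%, not exactly to it. It does not rescue a threshold curve with no effect at 45 mg (18% before, 20% after), because all three models are monotone.

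The least that would serve is to label every interval in Table 2.4 and Figure 2.4 as conditional on the selected model and report the selection frequencies. That discloses the problem without repairing it.

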## 9. EXPLORATORY STATISTICAL ANALYSES

### 9.1. Overview of Planned Exploratory Analyses

The exploratory analyses will be based on the ITT population, unless otherwise specified.

Table 10 provides an overview of the planned exploratory analyses, with full details of data displays being presented in Appendix 10: List of Data Displays.

**Table 10 Overview of Planned Exploratory Analyses**

[Endpoint / Parameter/ Display Type]	Absolute						Change from Baseline					
	Stats Analysis			Summary		Individual	Stats Analysis			Summary		Individual
	T	F	L	T	F	F	T	F	L	T	F	F
Efficacy Endpoints												
ACR 20/50/70 response												
Proportion at each assessment				Y	Y		Y					
DAS28(ESR)												
Values				Y			Y			Y	Y	
Longitudinal data analysis								Y	Y			
SDAI, CDAI and FACIT-Fatigue												
Values				Y			Y			Y	Y	
Longitudinal data analysis								Y	Y			
Categorical DAS28(CRP) / DAS28(ESR) response												
DAS28(CRP) / DAS28(ESR) remission												
Proportion at each assessment				Y			Y					
Other endpoints												
Swollen (28, 66) & Tender (28, 68) Joint Count				Y			Y			Y		
Patient's Assessment of Arthritis Pain (current pain/past week's pain)				Y			Y			Y		
Patient's Global Assessment of Arthritis				Y			Y			Y		
Physician's Global Assessment of Arthritis				Y			Y			Y		
CRP, ESR				Y			Y			Y	Y	
HAQ-DI score				Y			Y			Y	Y	

**NOTES :**

- T = Table, F = Figure, L = Listing, Y = Yes display generated, HAQ-DI: Health Assessment Questionnaire Disability Index
- Stats Analysis = Represents TFL related to any formal statistical analyses (i.e. modelling) conducted.
- Summary = Represents TFL related to any summaries (descriptive statistics) of the observed raw data.
- Individual = Represents FL related to any displays of individual subject observed raw data.

### 9.1.1. ACR 20/50/70 response

The number and percentage of responder will be presented. The difference of response rate from Placebo and the associated 95% CI will be calculated. The 95% CI will be based on normal approximation.

The percentage of ACR 20/50/70 responder by dose group will be plotted, respectively.

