4. STUDY DESIGN

4.1. Overall Design

- This is a randomized, double-blind, parallel group, 3 dosage level, placebo-controlled, Phase 1/2 study with the objective to assess pharmacokinetics, safety, tolerability and efficacy of GSK3196165 for 12 weeks, in combination with methotrexate (MTX), in Japanese subjects with active moderate-severe RA despite treatment with MTX.
- Approximately 40 subjects will be randomized into the study (10 subjects in each treatment groups).

Figure 1 Study Design

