9.2. Sample Size Assumptions

The sample size is determined based on feasibility. A total of 40 subjects will be randomized in a 1:1:1:1 proportion to receive GSK3196165 doses of 45 mg, 90 mg, 180 mg or placebo.

[Table 4](#) provides the precision of percentage of subjects with specific adverse events in each group with 10 subjects.

Table 4 Precision of percentage of subjects with specific adverse events in each group with 10 subjects

Number of subjects	Number of particular safety events observed	Exact 95% confidence intervals
10	1	0.3% - 44.5%
10	2	2.5% - 55.6%
10	3	6.7% - 65.2%

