### 11.6.2. Handling of Missing Data

Element	Reporting Detail
General	
 
Missing data occurs when any requested data is not provided, leading to blank fields on the collection instrument : 
 
These data will be indicated by the use of a “blank” in subject listing displays. Unless all data for a specific visit are missing in which case the data is excluded from the table.
 
Answers such as “Not applicable” and “Not evaluable” are not considered to be missing data and should be displayed as such.
 
 
 

Binary variable	
 
Subjects with missing efficacy data or early withdrawal will be imputed as a failure (e.g. no DAS28(CRP) remission or no moderate/good EULAR response).
 

Continuous variable	
 
No imputation will be done.
 

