**11.7. Appendix 7: Multiple Comparisons & Multiplicity**

No multiplicity adjustment will be planned because no formal statistical hypotheses will be tested in this study.

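### The 95% CIs for ACR, EULAR and remission differences rest on an unspecified normal approximation with about 10 subjects per arm. Read as Wald, they collapse to zero width at 0/10 vs 0/10 and miss a true zero difference about 9% of the time at equal rates of 20-30%.

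*SAP*

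**What the plan says.** SAP 9.1.1 plans, for ACR20, ACR50 and ACR70, the number and percentage of responders, and adds: "The difference of response rate from Placebo and the associated 95% CI will be calculated". The method is given in one sentence, "The 95% CI will be based on normal approximation", which 9.1.4 (EULAR response) and 9.1.5 (DAS28 remission) repeat. No section of the SAP says whether the variance is pooled, whether a continuity correction applies, or what to do when a cell is zero.

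SAP Table 10 lists these endpoints as "Proportion at each assessment". On numbers, Protocol 4.1 says "Approximately 40 subjects will be randomized into the study (10 subjects in each treatment groups", and Protocol 9.2 says "The sample size is determined based on feasibility". No expected response rates are given. SAP 11.6.2 says of binary endpoints: "Subjects with missing efficacy data or early withdrawal will be imputed as a failure". SAP 11.7 says: "No multiplicity adjustment will be planned because no formal statistical hypotheses will be tested in this study".

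**The concern.** A normal approximation to a difference of two proportions is unreliable at about 10 per arm, above all when counts are near 0 or 10. Low counts are realistic here. ACR70 and remission are demanding endpoints. Entry requires a screening DAS28(CRP) of at least 3.2, while remission means below 2.6 and is assessed from Week 1. Counting missing data and withdrawals as failure lowers the rates further.

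Because no test is planned, the interval is the only statement of uncertainty a reader gets for these differences. If it is too short or has no width, the display claims more than 20 subjects can support. If the variant is left to the programmer, the same data can appear to exclude zero or not.

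The number of intervals is not small. Tables 2.5-2.7 and 2.20-2.23 cover 7 responder endpoints. There are 3 dose contrasts and 7 scheduled post-baseline efficacy visits (Weeks 1, 2, 4, 6, 8, 12 and 22), and 7 x 3 x 7 = 147. This count infers from Table 10 that the difference is computed at every visit.

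**Working it through.** **Inputs.** n = 10 per arm (Protocol 4.1 and 9.2), two-sided 95% (SAP 9.1.1), z = 1.96. True response rates are assumptions; the documents supply none.

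**The plan's own figure.** Protocol Table 4 gives exact 95% intervals for single proportions at n = 10. The Clopper-Pearson limits, Beta(0.025; x, n-x+1) and Beta(0.975; x+1, n-x), give 0.25-44.50%, 2.52-55.61% and 6.67-65.25% for x = 1, 2 and 3. These match Table 4. So at this sample size the protocol uses exact intervals for adverse events but the SAP a normal approximation for response.

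**Readings of normal approximation**, with d = p1 - p0:

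- Wald, unpooled and uncorrected: d ± 1.96 √[p1(1-p1)/10 + p0(1-p0)/10]
- Continuity-corrected Wald: the same, widened by ½(1/10 + 1/10) = 0.10 on each side
- Pooled variance: d ± 1.96 √[p̄(1-p̄)(2/10)]

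**Example, 3/10 vs 0/10** (d = 0.30):

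- Wald: √(0.3 x 0.7/10) = 0.145, and 1.96 x 0.145 = 0.284, giving +1.6% to +58.4%.
- Continuity-corrected: -8.4% to +68.4%.
- Pooled: p̄ = 0.15, √(0.15 x 0.85 x 0.2) = 0.160, giving -1.3% to +61.3%.
- Newcombe: -3.8% to +60.3%. Miettinen-Nurminen (MN): -3.2% to +61.0%.

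**Example, 0/10 vs 0/10.** Wald and pooled both give 0 to 0. Continuity-corrected gives -10% to +10%, Newcombe -27.8% to +27.8% and MN -28.8% to +28.8%. At equal rates the chance of 0/10 vs 0/10 is (1-p)^20: 0.95^20 = 35.8% at a 5% rate, 12.2% at 10% and 1.2% at 20%.

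**Zero excluded when the true rates are equal.** All 11 x 11 = 121 outcomes were enumerated with their exact binomial probabilities.

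| True rate, both arms | Wald | Newcombe or MN |
|---|---|---|
| 5% | 1.4% | 0.1% |
| 10% | 5.0% | 0.9% |
| 20% | 9.1% | 3.0% |
| 30% | 9.5% | 3.7% |
| 50% | 8.8% | 4.2% |

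At 20-30% the continuity-corrected version excludes zero 1.1-2.6% of the time and the pooled version 3.0-3.7%. For arm sizes between 8 and 11, Wald stays at 7.6-10.2% over the same rates.

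**Where the excess comes from.** Wald excludes zero and both score intervals include it at 3/10 vs 0/10, 5/10 vs 1/10, 6/10 vs 2/10, 8/10 vs 4/10, 9/10 vs 5/10 and 10/10 vs 7/10. Counted in both directions, these outcomes have probability 6.1% at a common rate of 20% and 5.8% at 30%. That is the whole gap: 9.1 - 3.0 = 6.1 and 9.5 - 3.7 = 5.8. With a continuity correction all six include zero.

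**Coverage of the true difference.**

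| Placebo vs active | Wald | Newcombe |
|---|---|---|
| 1% vs 5% | 45.8% | 99.99% |
| 5% vs 15% | 79.6% | 99.1% |
| 10% vs 20% | 87.5% | 97.7% |
| 30% vs 30% | 90.5% | 96.3% |
| 10% vs 30% | 93.9% | 95.3% |
| 30% vs 60% | 93.4% | 93.6% |
| 5% vs 5% | 98.6% | 99.9% |

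Over the 19 rate pairs examined, Newcombe covers 93.6-99.99% and MN 95.2-99.9%. Continuity-corrected Wald covers 89.2-100%.

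**The case against.** The strongest reply is that little hangs on these intervals. The endpoints are exploratory and no hypothesis is tested. DAS28(CRP), the secondary efficacy endpoint, is analysed by MMRM and a dose-response model with bootstrap intervals. Counts and percentages appear beside each interval, and Listings 46-48 show the subject-level results, so a 0-to-0 interval next to two zeros is visibly degenerate. This limits the priority of the point but does not make the intervals right.

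A second reply is that Wald is an assumption. That is fair: the 9% figure disappears with a pooled variance or a continuity correction, and zero width disappears with the latter. But the SAP does not say which is meant, and the choice decides whether outcomes such as 3/10 vs 0/10 exclude zero.

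Third, the worst coverage figures need almost no response in both arms. At moderate unequal rates Wald does nearly as well as Newcombe, as 30% vs 60% shows, and at equal rates of 10% or less it does not exclude zero too often. This stands. The problem lies at equal rates of about 15-50% and at low unequal rates, plus zero width when both rates are low.

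Fourth, the 147 intervals are strongly correlated. ACR20/50/70 are nested, and the CRP and ESR versions overlap. The count shows how widely the method is used; it is not a number of independent chances of error.

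Fifth, for EULAR response SAP 11.5.4 leaves a missing category missing, while 11.6.2 imputes failure and names EULAR response as an example. If the denominator did fall to 8 per arm, Wald would still exclude zero 7.6-8.2% of the time at equal rates of 20-30%.

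**Conclusion.** The concern holds. The SAP does not identify the interval, and its most usual reading is unsuitable at about 10 per arm. Non-coverage at a true difference of zero is close to twice the nominal 5% at equal rates of 20-30%, and the interval has no width when neither arm has a responder. These sizes rest on the Wald reading and on assumed rates. The finding that the method is unspecified, and that the choice alters displayed results, rests on neither. Excluding zero here means interval non-coverage, not a test error, since no test is planned. The effect is confined to exploratory displays, so this should be corrected but does not threaten the study's primary conclusions.

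**What to change.** In SAP 9.1.1, 9.1.4 and 9.1.5, replace the normal approximation with a named method: the Miettinen-Nurminen score interval for the difference in proportions, or the Newcombe hybrid score interval as an acceptable alternative. State one of them in all three sections. Both are defined at zero cells, so naming one also settles the continuity correction.

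The cost is one sentence in three places and one SAS option (PROC FREQ with RISKDIFF, CL=MN or CL=NEWCOMBE). No new data are needed. Intervals become wider at very low counts: for 1/10 vs 0/10 the width goes from 37.2 points to 59.4 (Newcombe) or 61.7 (MN). At mid-range counts they can be narrower: for 6/10 vs 3/10 it goes from 83.2 points to 71.9 or 78.6.
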